1.2 WILL THIS RESEARCH INVOLVE COLLABORATION WITH ANOTHER INSTITUTION?

No, go to question 1.3
 Yes, answer questions within table

IF YES

Provide the name of the institution [for institutions located overseas, please also provide name of country]:
Carilion Hospital

Indicate the status of this research project with the other institution's IRB:

Pending approval
 Approved
 Other institution does not have a human subject protections review board
 Other, explain: **Human subject activities covered in this protocol.**

Will the collaborating institution(s) be engaged in the research?

(<http://www.hhs.gov/ohrp/policy/engage08.html>)

No
 Yes

Will Virginia Tech's IRB review all human subject research activities involved with this project?

No, provide the name of the primary institution:
 Yes

Note: primary institution = primary recipient of the grant or main coordinating center

1.3 IS THIS RESEARCH FUNDED?

No, go to question 1.4
 Yes, answer questions within table

IF YES

Provide the name of the sponsor [if NIH, specify department]: NIH/National Institute on Drug Abuse

Is this project receiving federal funds?

No
 Yes

If yes,

Does the grant application, OSP proposal, or “statement of work” related to this project include activities involving human subjects that are not covered within this IRB application?

- No, all human subject activities are covered in this IRB application
- Yes, however these activities will be covered in future VT IRB applications, these activities include:
 - Yes, however these activities have been covered in past VT IRB applications, the IRB number(s) are as follows:
 - Yes, however these activities have been or will be reviewed by another institution’s IRB, the name of this institution is as follows:
- Other, explain:

Is Virginia Tech the primary awardee or the coordinating center of this grant?

- No, provide the name of the primary institution:
- Yes

1.4 DOES THIS STUDY INVOLVE CONFIDENTIAL OR PROPRIETARY INFORMATION (OTHER THAN HUMAN SUBJECT CONFIDENTIAL INFORMATION), OR INFORMATION RESTRICTED FOR NATIONAL SECURITY OR OTHER REASONS BY A U.S. GOVERNMENT AGENCY?

For example – government / industry proprietary or confidential trade secret information

- No
- Yes, describe:

1.5 DOES THIS STUDY INVOLVE SHIPPING ANY TANGIBLE ITEM, BIOLOGICAL OR SELECT AGENT OUTSIDE THE U.S.?

- No
- Yes

Section 2: Justification

2.1 DESCRIBE THE BACKGROUND, PURPOSE, AND ANTICIPATED FINDINGS OF THIS STUDY:

Abuse liability of reduced nicotine content cigarettes: Experiment 1

IRB

v.8

03/15/2019

With the recently acquired mandate of the FDA to regulate the rapidly increasing market of tobacco products, research that can inform these regulations is vital. Before modifying the tobacco product marketplace through regulatory action, it is important to understand how specific features of tobacco products influence the choices to purchase and consume that product. The long-term goal of this line of research is to build an evaluative framework to assess how different aspects of tobacco products that may be subject to regulatory action (e.g., flavor, nicotine content, packaging) influence decisions to purchase and consume those products across a range of prices. To craft effective regulations, it is important to understand how specific features of tobacco products that may be subject to regulatory action influence the choice to purchase and consume that product.

Economic demand analyses quantify the relationship between the cost of a commodity and population-level measures of consumption of that commodity. Behavioral economic demand analyses are analogous to these population-level analyses, but can be used to understand the level of motivation to consume a product on either an individual or small group level, including cigarettes (Bickel et al., 1995; MacKillop et al., 2008). This level of analysis allows for experimental manipulations to be made on variables of interest. By quantifying how consumption decreases as costs to obtain and consume a product increase, important indices of demand are obtained. These indices can be grouped into two main measures of consumption,

demand intensity and demand elasticity, which are associated with use level and dependence severity (MacKillop et al., 2008, 2009, 2010; Murphy et al., 2011). Demand intensity is the amount of the commodity consumed when available at a very low cost approaching free, and demand elasticity quantifies the degree to which the individual is willing to increase monetary or effort-based expenditures to maintain the same level of consumption as costs increase. Elasticity of demand has been shown to be a characteristic of the drug itself and independent of drug dose for many drugs including nicotine (Bickel et al., 1991; Hursh & Roma, 2013; Hursh & Silberberg, 2008; Hursh & Winger, 1995).

While drug demand plotted as a function of unit price has been often shown to be a function of the total drug consumed, there is some research with cigarette demand that call this finding into question. The most prominent of these is a study by Johnson et al. (2004) that compared conventional cigarettes to denicotinized cigarettes. They found that, if they were the only tobacco product available, the denicotinized cigarettes had comparable demand to nicotinized cigarettes. If both were available, participants preferred the nicotinized cigarettes. This suggests that cigarette demand is not strictly regulated by nicotine dose, and that there is substantial abuse liability associated with the cigarettes themselves apart from any nicotine content.

The specific objective in the proposed research is to examine the effect of nicotine content (0.4 mg/g, 1.4 mg/g, 2.5 mg/g, 5.6 mg/g, and 17.4 mg/g of tobacco) and blood nicotine absorption on laboratory behavioral economic measures of demand intensity and elasticity. Under double-blind conditions, we will examine the relationship between plasma nicotine and cigarette demand as a function of the dose of the nicotine in the cigarettes. Regular cigarette smokers will consume, on separate sessions, controlled puffs of a cigarette containing a blinded dose of nicotine then complete a cigarette purchase task, our measure of value, while plasma nicotine is measured. We hypothesize that cigarette demand will be associated with dose and level of circulating nicotine, but in a nonlinear fashion such that consumption of very low dose cigarettes will not be predicted by nicotine dose or intake alone.

2.2 EXPLAIN WHAT THE RESEARCH TEAM PLANS TO DO WITH THE STUDY RESULTS:

For example - publish or use for dissertation

The research team intends to publish the results of the current study in peer-reviewed journals.

Section 3: Recruitment

3.1 DESCRIBE THE SUBJECT POOL, INCLUDING INCLUSION AND EXCLUSION CRITERIA AND NUMBER OF SUBJECTS:

Examples of inclusion/exclusion criteria - gender, age, health status, ethnicity

Up to 250 current cigarette smokers will be recruited from the community surrounding Roanoke, VA. Eligible participants will be 18 to 65 years old, smoke at least 5 cigarettes per day, have a breath carbon monoxide (CO) level of at least 10 ppm at intake, and have no immediate plans to quit smoking. Females who are planning pregnancy, pregnant, lactating, not willing to use contraception during the study, and individuals who weigh less than 110 lbs or who have plans to move out of the area during the course of the experiment will be excluded from participation. Use of other tobacco/nicotine products will not be exclusionary. These minimally restrictive inclusion/exclusion criteria will allow for a broad range of participants and increase the generalizability to tobacco regulation of our eventual results. Individuals who do not meet these eligibility criteria may be rescreened to see if they are eligible after at least 30 days has passed.

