For Aim 1 we request a sample size of $n=36$ completed participants. In this aim, we intend to compare demand for cigarettes across doses of nicotine. Typically, demand for a drug is not compared across doses because when price is expressed as unit dose (expenditure per mg of drug), all reinforcing doses of a drug fall on the same demand curve (Hursh & Silberberg, 2008). However, here we are explicitly intending to assess where the low-dose effect occurs for cigarettes (i.e., the dose at which consumption data no longer falls on the same unit-price curve), so we will compare demand across doses. A reanalysis of previous work (Johnson, et al., 2004) that compared demand for conventional and denicotinized cigarettes resulted in a very large effect size, which would be expected with cigarettes containing negligible amounts of nicotine. These data do not form a good basis for the present power analysis as they are an extreme case. Therefore, we have powered Experiment 1 to give us an 80% chance to detect an effect size of $f = 0.175$, which lies half way between a 'medium' and 'small' effect by convention (Cohen, 1992). This analysis was based on a within-factors ANOVA with 6 repeated measures (doses) per subject and a type 1 error rate of $\alpha = 0.05$, calculated in G*Power 3.1.9.2.

Data Analyses

Demand Analyses by Nicotine Content. In this experiment, we will compare behavioral economic demand intensity and elasticity of conventional cigarettes and reduced-nicotine cigarettes at five doses (0.4 mg/g, 1.4 mg/g, 2.5 mg/g, 5.6 mg/g, and 17.4 mg/g). Demand data will be fit to a modification (Koffarnus, et al., 2015) of a model proposed by Hursh and Silberberg (2008) to quantify the relationship between the price of a commodity and consumption of that commodity:

$$Q = Q_0 * 10^{k(e^{-\alpha Q_0 C} - 1)}$$

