where Q is consumption of the commodity, C is the price, Q_0 is the derived initial consumption without cost constraints (demand intensity), k is the span of the function in logarithmic units, and α is the demand elasticity. Q and C are determined by the data and k is set to a constant determined empirically by the actual data, leaving only Q_0 (demand intensity) and α (demand elasticity) as free parameters to be fitted. Analysis will proceed by fitting the above equation to individual subject data, then comparing demand intensity and elasticity consistent with the goals of each analysis. Intensity and elasticity from the demand function will be compared among the different cigarette types with nonlinear regression, as we have done previously (e.g., Koffarnus, Hall, et al., 2011; Koffarnus, et al., 2015). Then, mixed effects models will be used to characterize intensity and elasticity as a function of cigarette type. A random effect will be included to model repeated measures on subjects, and socio-economic and other demographic variables will be statistically screened for inclusion using

model-based hypothesis tests. These analyses will allow us to detect which doses fall on the same unit price curve and which doses do not and constitute a low-dose exception that we hypothesize will be related to lack of abuse liability. Additionally, we will be able to inform regulators how cigarettes at different doses are likely to affect unrestricted consumption (demand intensity) and cigarette valuation (demand elasticity).

In addition to the demand data, we will compare the VAS measures of drug effect as a function of cigarette dose to determine if these measures coincide with demand intensity, demand elasticity, or both. For these analyses, we will use mixed effects models to compare cigarette type and dose for the VAS measures and to control for the variance associated to subject in this within-subject design.

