Analyses by Nicotine Absorption. We will also analyze the demand data as a function of pharmacokinetic parameters derived from the plasma nicotine data, allowing us to determine how nicotine absorption and circulating nicotine level affects demand intensity and elasticity. From the plasma nicotine curves, we can obtain measures of C_{max} (the peak plasma nicotine concentration) and the area under the plasma nicotine concentration curve, a measure of the total nicotine exposure over a given period of time. These measures will allow us to assess demand as a function of actual nicotine exposure and provide quantitative estimates of how abuse liability of cigarettes relates to nicotine exposure. Data analyses will be carried out similarly to those above, but with the pharmacokinetic variables derived from plasma nicotine levels being the basis of comparison across doses. This will allow us to calculate demand parameters in terms of plasma nicotine instead of potentially arbitrary units like puffs or cigarettes consumed. Expressing demand in terms of plasma nicotine is important as it will allow us to project what the relative abuse liability and consumption of cigarettes would be across a range of obtained nicotine concentrations, independent of particulars of nicotine delivery among users or cigarettes (i.e., control for nicotine absorption by the lungs, puff velocity, etc.). This information would be very valuable to regulators, as it would allow them to create policy based on nicotine dose.

Expected Results

Understanding how demand for nicotine products relates to nicotine content and nicotine absorption is important for the effective regulation of nicotine content. We expect that demand will be related to plasma nicotine levels and nicotine content of the cigarettes, but that this will not be a strict one to one relationship. We expect this relationship to be more straightforward between the 5.6 and 17.4 mg/g doses, but that this will become less clear and break down at small doses approaching 0 mg/g (i.e., a low-dose exception). In Specific Aim 1, we will quantify this relationship between dose and demand, which will also result in the quantification of the demand associated with cigarettes delivering negligible nicotine.

Experiment 2: Model Potential Regulatory Environments with our Experimental Tobacco Marketplace

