Participant retention may be a limitation. This study requires repeated laboratory visits with a period of nicotine abstinence preceding most visits in Experiment 1, which may be difficult for some participants to accomplish. We have experience successfully completing studies with similar lab visit requirements, and to counteract this difficulty, we have budgeted for a projected dropout rate appropriate for each experiment based on previous experiments conducted in our lab with similar visit and abstinence requirements.

Those that drop out in Experiment 1 may be more likely to be heavy smokers who find the abstinence criterion more difficult, which could bias our results. To mitigate this limitation, we will perform an analysis of participants who drop out versus those who remain enrolled to detect any demographic differences or nicotine product use pattern differences and incorporate any differences as covariates in our statistical analysis where appropriate.

Project Timetable

Over the course of the three-year grant period, Experiment 1 will be completed in year 1 and Experiment 2 will be completed in years 2 and 3. The first 2 months of Experiment 1 will be allocated toward preparing for this experiment (i.e., training staff, preparing standard operating procedures, purchasing supplies, etc.), allowing 10 months to recruit and run the estimated 58 participants needed to complete 36 participants, or an average of 5.8 participants per month. Data analysis and manuscript preparation for this experiment will be completed in year 2 concurrently with the running of Experiment 2. The first 2 months of Experiment 2 in year 2 will be allocated to preparing for this experiment, with the final 2 months of year 3 allocated toward data analysis and manuscript preparation, leaving 20 months to recruit and run the estimated 174 participants needed to complete 150 participants, or an average of 8.7 participants per month. Over the past 12 months, studies in our laboratory with cigarette smokers as participants maintained an average of 30.8 participants enrolled per month. This far exceeds our requirements for the proposed enrollment goals for the proposed Experiment 1 (5.8 per month) and Experiment 2 (8.7 per month), assuring that we will be able to obtain the requisite number of eligible participants.

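### Experiment 1's plasma nicotine analysis names no commercial-brand term and no within-person split of exposure, so preference for the usual brand, and to a smaller degree differences between smokers, can enter the nicotine slope

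*Combined protocol and SAP*

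**What the plan says.** The objective is in section 2.1 of the Experiment 1 application: "we will examine the relationship between plasma nicotine and cigarette demand as a function of the dose of the nicotine in the cigarettes".

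The methods are in the research-plan text at the end of the combined document, under Data Analyses.

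- **Demand Analyses by Nicotine Content.** The demand curve is fitted to each subject. Intensity and elasticity are then modelled by cigarette type in mixed models: "A random effect will be included to model repeated measures on subjects". Socio-economic and demographic covariates enter if they pass a statistical screen. The compared products are conventional cigarettes and the five research contents.
- **Analyses by Nicotine Absorption.** Demand is analysed against peak plasma nicotine and area under the curve, "allowing us to determine how nicotine absorption and circulating nicotine level affects demand intensity and elasticity". The models are described only as similar to the preceding ones, with the plasma measures as the basis of comparison across doses. The section adds that expressing demand in plasma nicotine terms will allow projections that do not depend on how individual users or cigarettes deliver nicotine, and that regulators could use these for policy.

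Section 5.1 of the Experiment 1 application makes the usual brand one of the session products. It also adds a commercial cigarette of another brand, always given in session 7 and so outside the randomised order.

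**The concern.** Plasma nicotine differs between sessions of one smoker, largely because the research cigarettes differ in content by design. It also differs for two reasons that the design does not control: smokers absorb different amounts, and the usual brand differs from a research cigarette in more than nicotine.

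The brand problem is the larger. Section 2.1 itself says that cigarettes carry substantial abuse liability apart from their nicotine. The usual brand sits at the high-nicotine end: section 5.1 of the Experiment 2 application puts conventional cigarettes at about 16-19 mg/g. If smokers value it for taste or familiarity, the model sees high demand at high nicotine. Blinding to dose does not remove familiarity with taste.

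The smoker problem is smaller. If people who absorb more also value cigarettes more, a single slope mixes that association with the within-person relation.

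At stake is a reported effect of nicotine exposure on abuse liability that is partly, or in the worst case wholly, an effect of brand.

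**Working it through.** **1. The plan's own figure.** "For Aim 1 we request a sample size of $n=36$ completed participants", based on a "within-factors ANOVA with 6 repeated measures (doses) per subject", with 80% power at f = 0.175 and alpha 0.05. With correlation 0.5 and sphericity assumed (neither is stated), the noncentrality is f² × n × m / (1 − ρ) = 0.030625 × 36 × 6 / 0.5 = 13.23 on 5 and 175 degrees of freedom. Power is 0.7997, so the figure reproduces. It concerns the dose comparison. No power is stated for the plasma nicotine analysis.

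**2. Between-smoker share of a random-intercept slope.** The weight on the between-smoker slope is ψ·SSB / (ψ·SSB + SSW), where

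- ψ = (1 − ρ) / (1 − ρ + mρ)
- SSB = (n − 1)(m·ICC + 1 − ICC)
- SSW = n(m − 1)(1 − ICC)

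Here n = 36 and m = 6. The within-person correlation of demand ρ and the intraclass correlation of exposure (ICC) are assumed.

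- ρ = 0.5, ICC = 0.3: ψ = 0.143, SSB = 35 × 2.5 = 87.5, SSW = 36 × 5 × 0.7 = 126. Weight = 12.5 / 138.5 = 9%. With no subject term it would be 87.5 / 213.5 = 41%.
- ρ = 0.7, ICC = 0.1: 3.5 / 165.5 = 2%.
- ρ = 0.3, ICC = 0.7: 44.1 / 98.1 = 45%.

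The subject effect therefore removes most of the between-smoker contribution, but not all of it.

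**3. The brand part, by hand.** Use nicotine content as a stand-in for plasma nicotine: 0.4, 1.4, 2.5, 5.6 and 17.4 mg/g, plus the usual brand at an assumed 17.5. The mean is 44.8 / 6 = 7.467. The sum of squares about the mean is 648.74 − 334.51 = 314.23. Suppose nicotine has no effect and the usual brand carries a preference δ. The within-person slope is then δ × (17.5 − 7.467) / 314.23 = 0.032δ per mg/g. From 0.4 to 17.4 mg/g this is 17 × 0.0319δ = 0.54δ. About half of the brand preference would appear as a difference between the lowest and highest research cigarettes, although none exists. Centring on the person's mean leaves this slope unchanged, because it is already a within-person slope.

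**4. Simulated false-positive rates.** 36 people, no true within-person nicotine effect, nominal 5%. Assumed: plasma nicotine proportional to content times a personal factor with CV 50-80%, within-person demand correlation 0.3-0.7, and correlation of the personal factor with demand as shown.

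| Situation | Random intercept, plasma measure only | After correction |
|---|---|---|
| Neither smoker nor brand related to demand | 4% | – |
| Smokers only, five research cigarettes, correlation 0.3-0.7 | 4-13% (linear), 5-18% (log) | centred: 4-7% |
| Usual-brand preference 0.2-0.5 SD, six types | 14-52% | centred only: 12-47%; with brand term: 4-6% |
| Both, correlation 0.5 | 27-69% | centred plus brand term: 4-6% |

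The second row treats the variance ratio as known. Other runs over the same ranges reached 21% (linear) and 32% (log), but rates of 20-30% needed correlation 0.7 with CV 80%. At CV 50% and both correlations 0.5, the rate was about 8-10%.

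**The case against.** The strongest reply is that the plan never writes the criticised model. It refers back to the previous analyses, says a random effect rather than a random intercept, and speaks of comparison across doses, which could mean the five research contents alone. This stands in part: pooling of all cigarette types is an inference. It is the natural one, because the sample-size text counts six repeated measures as doses, and that number is reached only with the conventional cigarette.

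A reader might infer that a subject effect is the plan's only adjustment, and that differences between smokers are simply reported as an effect of nicotine. The documents do not support that. Demographic covariates are screened, and Difficulties and Limitations adds covariates where dropouts differ from completers. None of these codes brand or separates the two slopes, but the random effect does discard most of the between-smoker contribution. Fixed puff number and timing and CO-verified abstinence (section 5.1), and the 60 mL puffs with volume feedback in the research-plan text, should reduce it further.

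A reader might also infer that the plan promises a slope free of confounding. The sentence about user and cigarette differences concerns expressing demand in plasma nicotine units, so it makes no direct claim about a regression slope. Even so, projecting demand over obtained nicotine concentrations needs a relation that brand has not distorted.

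Finally, a flat dose profile in the content analysis would expose a false exposure effect. That is a useful cross-check if the research cigarettes are examined separately, but the plan does not make the exposure conclusion depend on it.

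**Conclusion.** The concern holds, chiefly as a brand problem. If the usual brand enters the plasma nicotine model without a term of its own, a preference of 0.2 to 0.5 SD gives roughly 14-50% false positives when nicotine has no effect, and the subject effect offers no protection. The between-smoker part is secondary: about 5-10% at moderate settings and about 20-30% only at extreme ones.

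All of these sizes rest on assumed brand preference, variation in absorption and correlations. The documents give none of them, so the figures show direction and possible size and do not forecast the bias in this trial. Nor do the documents say that the usual brand is included in this analysis. If the analysis were confined to the five research cigarettes, the brand part would vanish and only the smaller part would remain. The point should be settled before the exposure analysis is run. It does not affect the sample size, which was set for the dose comparison.

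**What to change.** Under Analyses by Nicotine Absorption, write out the model and state which cigarettes enter it.

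1. Make the exposure-demand slope on the five research cigarettes the main analysis, or keep the usual brand and add a commercial-brand indicator. Show the usual-brand sessions and the non-randomised session-7 sessions as reference points. If both commercial products are modelled, give each its own term, because a single indicator would treat the preferred and the non-preferred brand alike.
2. Split each plasma measure into the participant's mean over the sessions in the model and the session's deviation from that mean. Enter both, base the conclusion on the deviation slope, and report the between-person slope separately.
3. State that the deviation slope still includes session-to-session differences in inhalation. Plasma nicotine is measured after the cigarette is smoked, and only cigarette order is randomised.

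Both 1 and 2 are needed: centring alone leaves the brand part, and a brand term alone leaves the smoker part.

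The cost is analysis wording, one derived variable per plasma measure and a slightly wider interval for the slope. No new data are needed. The six-type dose comparison and its 36 completers are untouched. Only if that comparison were also cut to five types would its power at 36 fall, to 74.7% (noncentrality 0.030625 × 36 × 5 / 0.5 = 11.03), with 41 completers needed for 80%.
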